Table 4 Study SPR001-204 Protocol Schedule of Optional Open-Label Extension Period Activities

	Extension Treatment Period												Follow-up	ET
	1	2	3	4	5	6	7	8	9	10	11	12	13	
STUDY VISIT NUMBER	533	617	701	869	1037	1205	1373	1541	1709	1877	2046	2213	Last dose +30 days	
STUDY WEEK	76	88	100	124	148	172	196	220	244	268	292	316	320	
STUDY DAY ¹	533	617	701	869	1037	1205	1373	1541	1709	1877	2046	2213		
Study Visit (V)	V	V	V	V	V	V	V	V	V	V	V	V	V	V
Urine pregnancy test for FCP	X	X	X	X	X	X	X	X	X	X	X	X	X	X
Hormones from blood ^{2,3}	X	X	X	X	X	X	X	X	X	X	X	X		X
Clinical laboratory ²	X	X	X	X	X	X	X	X	X	X	X	X		X
Vital signs ⁴ , body weight, waist circumference	X	X	X	X	X	X	X	X	X	X	X	X		X
SF-36				X		X		X		X		X		X
C-SSRS				X		X		X		X		X		X
Scrotal ultrasound for males ⁵				X		X		X		X		X		X ⁵
DXA scan for body composition and bone mineral density ⁶				X		X		X		X		X		X
Concomitant medications	X	X	X	X	X	X	X	X	X	X	X	X	X	X
Review adverse events	X	X	X	X	X	X	X	X	X	X	X	X	X	X
Abbreviated physical examination	X			X		X		X		X		X		X
Dispense study drug ⁷	X	X	X	X	X	X	X	X	X	X	X	X		
Study drug accountability	X	X	X	X	X	X	X	X	X	X	X	X		X

¹ All study visits should be performed within a +30-day window after the indicated study days.

² Samples for these lab assessments will be obtained at 8 AM ± 1 hour, after an overnight fast (nothing to eat after midnight) and before any morning dose of GC medication. On the evenings before scheduled laboratory assessments, subjects should take their evening GC dose before 10 PM.

³ A4 and 17-OHP and testosterone will be measured.

⁴ Vital signs consist of systolic and diastolic blood pressure, pulse rate, body temperature, and respiration rate and will be measured after a 5-min rest period.

⁵ Scrotal ultrasounds will only be conducted in subjects who had TART(s) at baseline.

⁶ DXA scans should be performed for all subjects as indicated. Subjects should not take calcium supplements within the 24 hours before a DXA scan.

⁷ Either the subject will pick up study drug in the clinic or the study drug will be shipped directly to the subject. Study drug will be taken daily between 6 PM and midnight, with an evening meal. The evening meal should contain <50% fat content. Study drug may be consumed up to 30 minutes after completing the evening meal, if necessary.

STUDY VISIT NUMBER	Extension Treatment Period												Follow-up	ET	
	1	2	3	4	5	6	7	8	9	10	11	12	13		
STUDY WEEK	76	88	100	124	148	172	196	220	244	268	292	316	320		
STUDY DAY ¹	533	617	701	869	1037	1205	1373	1541	1709	1877	2046	2213	Last dose +30 days		
Study Visit (V)	V	V	V	V	V	V	V	V	V	V	V	V	V	V	V
GC dose adjustment telephone contacts ⁸	X	X	X	X	X	X	X	X	X	X	X				
Dispense HC for stress dosing and perform accountability ⁹	X	X	X	X	X	X	X	X	X	X	X				X

17-OHP = 17 hydroxyprogesterone; A4 = androstenedione; ACTH = adrenocorticotrophic hormone; ALP = alkaline phosphatase; ALT = alanine aminotransferase; AST = aspartate aminotransferase; BSAP = bone-specific alkaline phosphatase; CGI-I; Clinical Global Impression – Improvement Scale; C-SSRS = Columbia–Suicide Severity Rating Scale; CTX-1 = C-terminal telopeptide of type 1 collagen; DXA = dual-energy x-ray absorptiometry (scan); EC = Ethics Committee; ECG = electrocardiogram; EDC = electronic data capture; ET = early termination; FCP = female of childbearing potential; FSH = follicle-stimulating hormone; GC = glucocorticoid; GGT = gamma-glutamyltransferase; HADS = Hospital Anxiety and Depression Scale; HbA1c = hemoglobin A1c; HC(e) = hydrocortisone (equivalents); HOMA-IR = homeostatic model assessment of insulin resistance; INR = international normalized ratio; IRB = Institutional Review Board; LH = luteinizing hormone; LLD = lower limit of detection; P1NP = procollagen type 1 N terminal propeptide; PGIC = Patient Global Impression of Change; PK = pharmacokinetics; PRN = as needed; PROs = patient-reported outcome measures; PT = prothrombin time; PTT = partial thromboplastin time; SF-36 = Short Form 36; SHBG = sex hormone–binding globulin; T = telephone contact; TART = testicular adrenal rest tumor; ULN = upper limit of normal; U-NTx = urinary N-linked telopeptide of type 1 collagen; V = study visit

⁸ During the Treatment Period, sites will make telephone contacts to subjects who are eligible for a GC dose adjustment within 2 weeks after each applicable study visit and based on their A4 level at that visit. Subjects who are not eligible for a GC change will not be telephoned. The site will direct the subject to adjust his/her GC dose by no more than 5 mg/day HCe increments if the subject has not experienced any change in clinical status since the previous study visit. If a subject's GC dose is adjusted, the site will telephone the subject again 7 days after the GC dose adjustment to assess for the occurrence of AEs and the initiation of new concomitant medications. GC dose may be reduced to a minimum of 15 mg HCe per day (approximately physiologic replacement level).

⁹ Bottles of HC for stress dosing will be dispensed as needed. Accountability for bottles of HC will be performed at every study visit.

5 STUDY OBJECTIVES AND ENDPOINTS

The objectives of this study are to evaluate the efficacy and safety of tildacerfont in adult subjects with classic CAH who have $A4 \leq 2.5 \times ULN$ and are on supraphysiologic doses of GC therapy (≥ 30 mg/day and ≤ 60 mg/day in HCe) at baseline.

This study will evaluate the potential of tildacerfont to reduce GC burden (total daily GC dose, total GC exposure over 24 weeks) in adult subjects with classic CAH. Study SPR001-204 will characterize clinical outcomes after 1) 24 weeks of double-blind treatment, 2) 52 weeks of open label treatment with tildacerfont and 3) 76 weeks of treatment with tildacerfont to support the clinical relevance of observed changes in GC dose.

The optional Open-Label Extension Period will provide additional characterization of up to 240 weeks of treatment with tildacerfont on GC dose changes and changes in clinical outcomes. See [Table 5](#) for a summary of the study objectives and endpoints.

Table 5 SPR001-204 Study Objectives and Endpoints

Objectives	Endpoints		Analysis
1. Primary Efficacy			
To evaluate the mean absolute GC change in subjects with classic CAH over the 24-week, Double Blind, Placebo-Controlled Treatment Period	1.1	Absolute change from baseline in GC dose in HCe at Week 24	Primary Analysis
2. Secondary Efficacy			
To evaluate the effect of tildacerfont in reducing GC use to near-physiologic levels while maintaining androgen control in subjects with CAH	2.1	Proportion of subjects with GC dose ≤ 11 mg/m ² /day in HCe and $A4 \leq 1.2 \times$ baseline or $A4 \leq ULN$ at Week 24	Primary Analysis
To evaluate the effect of tildacerfont in reducing GC use to near-physiologic levels while maintaining androgen control in subjects with CAH	2.2	Proportion of subjects with baseline GC dose ≤ 35 mg HCe who achieve GC dose ≤ 11 mg/m ² /day in HCe and $A4 \leq 1.2 \times$ baseline or $\leq ULN$ at Week 24	Primary Analysis
To evaluate the effect of tildacerfont in reducing cardiovascular risk in subjects with CAH	2.3	Proportion of subjects with improvement in at least one cardiovascular risk factor at Week 24	Primary Analysis
3. Exploratory Efficacy			
To evaluate the percentage change in GC use in subjects with CAH	3.1	Percent change from baseline in GC dose at Week 24	Primary Analysis

Objectives		Endpoints	Analysis
To evaluate the effect of tildacerfont in reducing the cumulative HCe dose in subjects with CAH	3.2	Change in total cumulative GC dose in HCe at Week 24	Primary Analysis
To evaluate the effect of tildacerfont in improving HOMA-IR in subjects with CAH	3.3	Change from baseline in the HOMA-IR at Week 24	Primary Analysis
To evaluate the effect of tildacerfont in improving HOMA-IR after 52 weeks of tildacerfont treatment in subjects with CAH	3.4	Change from baseline in HOMA-IR after 52 weeks of tildacerfont treatment	Final Analysis
To evaluate the effect of tildacerfont in reducing cardiovascular risk in subjects with CAH	3.5	Proportion of subjects with improvement in at least one cardiovascular risk factor at Week 52	Final Analysis
To evaluate the effect of tildacerfont in reducing GC use to near-physiologic levels while maintaining androgen control in subjects with CAH	3.6	Proportion of subjects with GC dose $\leq 11 \text{ mg/m}^2/\text{day}$ and A4 $\leq 1.2 \times$ baseline or $\leq \text{ULN}$ at Week 52	Final Analysis
To evaluate the effect of tildacerfont in reducing GC use to near-physiologic levels while maintaining androgen control in subjects with CAH	3.7	Proportion of subjects with baseline GC dose $\leq 35 \text{ mg HCe}$ who achieve GC dose $\leq 11 \text{ mg/m}^2/\text{day}$ in HCe and A4 $\leq 1.2 \times$ baseline or $\leq \text{ULN}$ at Week 52	Final Analysis
To evaluate the effect of tildacerfont in improving quality of life in subjects with CAH	3.8	Change from baseline at Week 24 in the SF-36 domains and composite scores	Primary Analysis
To evaluate the effect of tildacerfont in improving quality of life in subjects with CAH	3.9	Change from baseline at Week 52 in the SF-36 domains and composite scores	Final Analysis
To evaluate the effect of tildacerfont on BMI after 24 weeks in subjects with CAH	3.10	Percent change from baseline in BMI at Week 24	Primary Analysis
To evaluate the effect of tildacerfont on BMI after 52 weeks of tildacerfont treatment in subjects with CAH	3.11	Percent change from baseline in BMI after 52 weeks of tildacerfont treatment	Final Analysis
To evaluate the effect of tildacerfont on waist circumference after 24 weeks of tildacerfont treatment in subjects with CAH	3.12	Change from baseline in waist circumference after 24 weeks of tildacerfont treatment	Primary Analysis
To evaluate the effect of tildacerfont on waist circumference after 52 weeks of tildacerfont treatment in subjects with CAH	3.13	Change from baseline in waist circumference after 52 weeks of tildacerfont treatment	Final Analysis
To evaluate the effect of tildacerfont in improving body composition after 24 weeks of tildacerfont treatment in subjects with CAH	3.14	Change from baseline in percent total fat mass and total percent lean mass after 24 weeks of tildacerfont treatment	Primary Analysis
To evaluate the effect of tildacerfont in improving body composition after 52 weeks of tildacerfont treatment in subjects with CAH	3.15	Change from baseline in percent total fat mass and total percent lean mass after 52 weeks of tildacerfont treatment	Final Analysis
To evaluate the effect of tildacerfont in improving BMD after 52 weeks of tildacerfont treatment in subjects with CAH	3.16	Change from baseline in BMD after 24 and 52 weeks of tildacerfont treatment	Primary (Week 24) and Final Analysis

Objectives		Endpoints	Analysis
To evaluate the effect of tildacerfont in reducing TART(s) in male CAH subjects with TART(s) at baseline after 24 weeks of tildacerfont treatment in subjects with CAH	3.17	Reduction in TART volume at Week 24 in male subjects who had TART(s) at baseline	Primary Analysis
To evaluate the effect of tildacerfont in reducing TART(s) in male CAH subjects with TART(s) at baseline after 52 weeks of tildacerfont treatment in subjects with CAH	3.18	Reduction in TART volume at Week 52 in male subjects who had TART(s) at baseline	Final Analysis
To evaluate the effect of tildacerfont in reducing GC use while maintaining normal A4 levels at Week 24 in subjects with CAH	3.19	Proportion of subjects with at least a 5 mg/day HCe reduction from baseline (Day 1) in GC dose and A4 $\leq 1.2 \times$ baseline or \leq ULN at week 24	Primary Analysis
To evaluate the effect of tildacerfont in reducing GC use while maintaining normal A4 levels at Week 52 in subjects with CAH	3.20	Proportion of subjects with at least a 5 mg/day HCe reduction from baseline (Day 1) in GC dose and A4 $\leq 1.2 \times$ baseline or \leq ULN at week 52	Final Analysis
4. Exploratory Efficacy (Optional Open-Label Extension Period) (Separate SAP)			
To evaluate the effect of tildacerfont in reducing GC use to near-physiologic levels in subjects with CAH	4.1	Proportion of subjects with GC dose $\leq 11 \text{ mg/m}^2/\text{day}$ in HCe and A4 \leq ULN at EOT	Separate SAP
To evaluate the percentage change in GC use in subjects with CAH	4.2	Percent change from baseline in GC dose at EOT	Separate SAP
To evaluate the effect of tildacerfont in reducing cardiovascular risk in subjects with CAH and at least one cardiovascular risk factor at baseline	4.3	Proportion of subjects with improvement in at least one cardiovascular risk factor at EOT	Separate SAP
To evaluate the effect of tildacerfont in improving BMD in subjects with CAH	4.4	Change from baseline in BMD at EOT	Separate SAP
To evaluate the effect of tildacerfont in reducing TART(s) in male CAH subjects with TART(s) at baseline	4.5	Proportion of male subjects with reduction TART(s) at EOT who had TART(s) at baseline	Separate SAP
5. Safety			
To evaluate the safety of tildacerfont in subjects with CAH	5.1	AEs, SAEs	Primary Analysis

5.1 Efficacy Objectives and Endpoints

5.1.1 Primary Efficacy Endpoint

The Primary Objective of the study is to evaluate the change in total daily GC dose in subjects with classic CAH over the 24-week, double blind, Placebo-Controlled Treatment Period. The Primary Efficacy Endpoint is the absolute change from baseline (Day 1) in GC dose in HCe at Week 24. The analysis of absolute change in total daily GC dose in HCe will include data from Weeks 3, 6, 12, 18 and 24 in a mixed model.

5.1.2 Secondary Efficacy Endpoints

The Secondary Efficacy Objectives and associated Secondary Efficacy Endpoints are provided in [Table 5](#). The Secondary Efficacy Endpoints are further described in the following sections.

5.1.2.1 GC use while maintaining androgen control at Week 24 with subjects with CAH

Secondary Efficacy Endpoint 2.1 evaluates the response to randomized treatment in terms of reducing GC to $\leq 11\text{mg mg/m}^2/\text{day}$ in HCe while maintaining androgen control, defined as A4 levels at approximately baseline ($\leq 1.2\times$ baseline) or within normal limits ($\leq \text{ULN}$) at Week 24 in subjects with CAH.

Secondary Efficacy Endpoint 2.2 is similar to 2.1 but evaluated in those subjects with baseline GC $\leq 35\text{ mg/m}^2/\text{day}$ in HCe.

5.1.2.2 Improving Cardiovascular Risk Factors at Week 24

Secondary Efficacy Endpoint 2.3 evaluates the effect of randomized treatment in reducing CV risk factors in classic CAH subjects at Week 24. The Secondary Efficacy Endpoint is the proportion of subjects who had improvement in at least one CV risk factor at Week 24. Only subjects CV risk factors at baseline will be included in the endpoint analysis.

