5.1.3 Exploratory Efficacy Endpoints

5.1.3.1 Percent Change in HCe Dose at Week 24

Exploratory Efficacy Endpoint 3.1 evaluates the effect of randomized treatment in reducing GC HCe dose in classic CAH subjects at Week 24 in mean percentage terms. This analysis will be achieved by examination of the change in daily GC HCe dose from baseline (Day 1) to post baseline visits on the log scale. Results will be back transformed to present the outcome as a percentage change.

5.1.3.2 Cumulative HCe Dose at Week 24

Exploratory Efficacy Endpoint 3.2 evaluates the effect of randomized treatment in reducing the cumulative HCe dose (total exposure in HCe mg) in classic CAH subjects over 24 Weeks. The endpoint is the cumulative GC dose in HCe from baseline (Day 1) at Week 24. Similar to endpoint 3.1, the endpoint will be analyzed on the log scale.

5.1.3.3 Change in HOMA-IR at Weeks 24 and 52

Exploratory Efficacy Endpoints 3.3 and 3.4 evaluate the effect of randomized treatment in improving HOMA-IR in classic CAH subjects at Weeks 24 and 52. The associated endpoints are the change in fasting HOMA-IR from baseline (Day 1) to Week 24 and Week 52.

5.1.3.4 Improving Cardiovascular Risk Factors at Week 52

Exploratory Efficacy Endpoint 3.5 evaluates the effect of randomized treatment in reducing CV risk factors in classic CAH subjects at Week 52. The endpoint is similar to Secondary Efficacy Endpoint 2.3, being the proportion of subjects who had improvement in at least one CV risk factor at Week 52. Only subjects CV risk factors at baseline will be included in the endpoint analysis.

5.1.3.5 GC use while maintaining androgen control at Week 52

Exploratory Efficacy Endpoints 3.6 and 3.7 are similar to the Secondary Efficacy Endpoints 2.1 and 2.2, but now assessed at 52 weeks. Secondary Efficacy Endpoints 3.6 is the response to randomized treatment in terms of reducing GC to $\leq 11\text{mg mg/m}^2/\text{day}$ in HCe while maintaining

androgen control, defined as A4 levels at approximately baseline ($\leq 1.2x$ baseline) or within normal limits (\leq ULN) at Week 52 in subjects with CAH.

Exploratory Efficacy Endpoint 3.7 is similar to 3.6 but evaluated in those subjects with baseline GC ≤ 35 mg/m²/day in HCe.

5.1.3.6 Quality of Life at Week 24 and Week 52

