8.3.14 Responder Definitions

Where Efficacy Endpoints are proportions of responders based on serum hormone assessments, GC dose, and/or CV risk factors, indicator variables will be created as [Table 9](#).

Table 9 Responder Definition by Endpoint

Endpoint	Definition
Proportion of subjects with GC dose ≤ 11 mg/m ² /day in HCe and A4 $\leq 1.2 \times$ baseline or A4 \leq ULN at Week 24	$1 = \text{Week 24 GC dose} \leq 11 \text{mg/m}^2/\text{day in HCe AND (A4} \leq 1.2 \times \text{baseline or A4} \leq \text{ULN})$ $0 = \text{otherwise}$
Proportion of subjects with baseline GC dose ≤ 35 mg HCe who achieve GC dose ≤ 11 mg/m ² /day in HCe and A4 $\leq 1.2 \times$ baseline or A4 \leq ULN at Week 24	$1 = \text{Baseline GC dose} \leq 35 \text{mg HCe AND Week 24 GC dose} \leq 11 \text{mg/m}^2/\text{day in HCe AND (A4} \leq 1.2 \times \text{baseline or A4} \leq \text{ULN})$ $0 = \text{otherwise}$
Proportion of subjects with GC dose ≤ 11 mg/m ² /day in HCe and A4 $\leq 1.2 \times$ baseline or A4 \leq ULN at Week 52	$1 = \text{Week 52 GC dose} \leq 11 \text{mg/m}^2/\text{day in HCe AND (A4} \leq 1.2 \times \text{baseline or A4} \leq \text{ULN})$ $0 = \text{otherwise}$
Proportion of subjects with baseline GC dose ≤ 35 mg HCe who achieve GC dose ≤ 11 mg/m ² /day in HCe and A4 $\leq 1.2 \times$ baseline or A4 \leq ULN at Week 52	$1 = \text{Baseline GC dose} \leq 35 \text{mg HCe AND Week 52 GC dose} \leq 11 \text{mg/m}^2/\text{day in HCe AND (A4} \leq 1.2 \times \text{baseline or A4} \leq \text{ULN})$ $0 = \text{otherwise}$
Proportion of subjects with at least a 5 mg/day HCe reduction from baseline (Day 1) in GC dose and A4 $\leq 1.2 \times$ baseline or \leq ULN at week 24	$1 = \text{Week 24 GC dose reduction from baseline} \leq -5 \text{mg/day in HCe AND (A4} \leq 1.2 \times \text{baseline or A4} \leq \text{ULN})$ $0 = \text{otherwise}$
Proportion of subjects with at least a 5 mg/day HCe reduction from baseline (Day 1) in GC dose and A4 $\leq 1.2 \times$ baseline or \leq ULN at week 52	$1 = \text{Week 52 GC dose reduction from baseline} \leq -5 \text{mg/day in HCe AND (A4} \leq 1.2 \times \text{baseline or A4} \leq \text{ULN})$ $0 = \text{otherwise}$
Proportion of subjects with ≥ 1 CV risk factor at baseline achieving an improvement in at least one CV risk factor at Week 24	$\begin{cases} 1 & \text{improvement in } \geq 1 \text{ baseline CV risk factor at Week 24} \\ 0 & \text{no improvement} \end{cases}$

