9.6 Type I Error Control

Type I Error control for the Secondary Efficacy Endpoints will be achieved by hierarchical testing. If the Primary Efficacy Endpoint is met, then Secondary Efficacy Endpoints displayed in [Table 5](#) will be evaluated using the Hochberg (1988) closed test procedure with an alpha of 0.05.

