9.7 Examination of Subgroups

Subjects will be categorized into the following common subgroups for the purposes of evaluating the Primary and Secondary Efficacy Endpoints.

- Sex (Male, Female)
- Baseline GC dose in HCe
 - < 40 mg/day, \geq 40 mg/day
 - < 35 mg/day (For endpoint 2.2 and 3.7 only)
- Baseline A4 levels (A4 \leq ULN, A4 $>$ ULN)

In addition, all potential subgroup x subgroup combinations are also pre-specified. If the primary analysis is positive, exploratory subgroup analysis for age, race, ethnicity, and region will be used to further evaluate the Primary and Secondary Efficacy endpoints.

Comparisons will only be provided for subgroups where each subgroup has at least 10 subjects. Additional subgroups specific to only select endpoints are specified in the appropriate section in the SAP.

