12.5 Secondary Efficacy Endpoint Analyses

The analysis population for the Secondary Efficacy Endpoint analyses is the ITT analysis set, including all classic CAH subjects who were randomized into the study.

Table 13 Secondary Efficacy Endpoints

Objectives		Endpoints	Analysis
Secondary Efficacy			
To evaluate the effect of tildacerfont in reducing GC use to near-physiologic levels while maintaining androgen control in subjects with CAH	2.1	Proportion of subjects with GC dose \leq 11 mg/m ² /day in HCe and A4 \leq 1.2x baseline or A4 \leq ULN at Week 24	Primary Analysis
To evaluate the effect of tildacerfont in reducing GC use to near-physiologic levels while maintaining androgen control in subjects with CAH	2.2	Proportion of subjects with baseline GC dose \leq 35mg HCe who achieve GC dose \leq 11 mg/m ² /day in HCe and A4 \leq 1.2x baseline or \leq ULN at Week 24	Primary Analysis
To evaluate the effect of tildacerfont in reducing cardiovascular risk in subjects with CAH	2.3	Proportion of subjects with improvement in at least one cardiovascular risk factor at Week 24	Primary Analysis

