12.5.1 Statistical Hypotheses for Secondary Efficacy Endpoints

For Secondary Efficacy Endpoint 2.1 the null hypothesis is that the difference between randomized treatment groups in the proportion of subjects achieving GC dose ≤ 11 mg/m²/day in HCe and A4 ≤ 1.2 times baseline or A4 \leq ULN at Week 24 is equal to zero. The alternative hypothesis is that the difference is not equal to zero.

For Secondary Efficacy Endpoint 2.2 the null hypothesis is that in the subset of subjects with a baseline GC dose ≤ 35 mg the difference between randomized treatment groups in the proportion of subjects achieving GC dose ≤ 11 mg/m²/day in HCe and A4 ≤ 1.2 times baseline or A4 \leq ULN at Week 24 is equal to zero. The alternative hypothesis is that the difference is not equal to zero.

Secondary Efficacy Endpoint 2.3 is the proportion of classic CAH subjects who were randomized into the study who improve at least one baseline CV risk factor at 24 weeks from randomization. This proportion is calculated for each treatment group (e.g., placebo, tildacerfont) as the number of subjects at Week 24 who had at least one CV risk factor at baseline (i.e. subjects without any CV risk factors will not be included in the analysis) and no longer meets one or more of the baselines CV risk factors at Week 24, divided by the total number of subjects in the ITT analysis who were randomized to that specific treatment and had at least one CV risk factor at baseline.

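### The subject set for secondary endpoint 2.2 (and exploratory 3.7) is given with three different baseline cuts in the SAP, and Table 9 leaves its denominator unclear

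*SAP*

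**What the plan says.** The reading that dominates is an absolute, inclusive cut. SAP Table 5 words endpoint 2.2 as "Proportion of subjects with baseline GC dose" ≤35 mg HCe who reach the Week 24 GC and A4 targets. Table 13, the figure list in 12.7 and the protocol (synopsis, Table 7, sections 3 and 9.6) agree. SAP 12.5.1 says "the null hypothesis is that in the subset of subjects with a baseline GC dose" ≤35 mg the two proportions are equal. For 3.7, the same cut appears in SAP Tables 5, 9 and 15 and in the protocol synopsis.

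The other places are these:

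- **SAP 5.1.2.1:** "Secondary Efficacy Endpoint 2.2 is similar to 2.1 but evaluated in those subjects with baseline GC" ≤35 mg/m²/day in HCe.
- **SAP 5.1.3.5:** "Exploratory Efficacy Endpoint 3.7 is similar to 3.6 but evaluated in those subjects with baseline" GC ≤35 mg/m²/day in HCe.
- **SAP 9.7:** the subgroup list has the entry "< 35 mg/day (For endpoint 2.2 and 3.7 only").
- **SAP Table 9 (8.3.14):** the indicator for 2.2 is 1 when baseline GC is ≤35 "mg HCe AND Week 24 GC dose" is ≤11 mg/m²/day and the A4 condition is met. Everyone else gets 0.
- **SAP 12.5:** the population for the secondary endpoints "is the ITT analysis set, including all classic CAH subjects who were randomized into the study".

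SAP 9.6 states that, once the primary endpoint is met, the secondary endpoints in Table 5 "will be evaluated using the Hochberg (1988) closed test procedure with an alpha of 0.05".

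**The concern.** Endpoint 2.2 belongs to the family with Type I error control, so who is counted should be the same wherever the plan describes it. Here the unit changes in one place and the inequality in another, and a third place could be programmed with a different denominator. The mg/m² cut lets in subjects the endpoint is meant to leave out. The strict cut removes subjects it is meant to keep. Coding subjects above the cut as 0 dilutes the reported response rates.

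Two features of the SAP stop it from resolving itself. The rule in section 3 that the SAP governs settles only conflicts between SAP and protocol, and this conflict lies within the SAP. Section 14, on changes from the protocol, is still to be completed. If the text stays as it is, the choice of subject set could be made, or appear to have been made, after unblinding. Under Hochberg, the 2.2 p-value can also change whether 2.1 and 2.3 are declared significant.

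**Working it through.** The documents give no planned size, power or response rate for 2.2 or 3.7, so there is no stated figure to reproduce. The thresholds follow from the documents. The shares, powers and p-values rest on assumptions, which are labelled.

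**Inputs.** Eligible baseline dose: 30 to 60 mg/day HCe (inclusion criterion 4; SAP section 4). Prednisolone factor: 5 (SAP Table 11). Dose step: 5 mg HCe (SAP 4.2.2.1). Randomised: 45 per arm (SAP section 6). Dose strata: <40 and ≥40 mg/day (SAP 4.1). Neither document gives a distribution of body surface area (BSA) or of dose.

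**1. The mg/m² cut.** A subject on dose d meets ≤35 mg/m² when d/BSA ≤ 35, that is, when BSA ≥ d/35. The two cuts coincide only at BSA 1.0 m².

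| Dose (mg/day) | Admitted at BSA of at least (m²) |
|---|---|
| 40 | 40/35 = 1.14 |
| 45 | 45/35 = 1.29 |
| 50 | 50/35 = 1.43 |
| 55 | 55/35 = 1.57 |
| 60 (eligibility cap) | 60/35 = 1.71 |

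Put the other way, the cut in mg/day is 35 × BSA: 52.5 at 1.5 m², 63 at 1.8 m² and 70 at 2.0 m². At 1.71 m² and above it excludes nobody who is eligible.

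*Assumed:* BSA normal with SD 0.2 m², and doses above 35 mg spread evenly over 40, 45, 50, 55 and 60 mg. The share of subjects above 35 mg who would be wrongly admitted is the average of P(BSA ≥ d/35) over those five doses:

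| Mean BSA (m²) | 1.5 | 1.6 | 1.7 | 1.8 | 1.9 |
|---|---|---|---|---|---|
| Share admitted | 59% | 72% | 82% | 90% | 95% |

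At the upper end, 2.2 is close to a repeat of 2.1.

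**2. The strict <35 cut.** Prednisolone 6, 7 and 8 mg are 6×5 = 30, 7×5 = 35 and 8×5 = 40 mg HCe, so 35 mg is an ordinary dose level. On a 5 mg grid the ≤35 subset holds doses 30 and 35; the <35 subset holds only 30.

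*Assumed:* 20 per arm at ≤35 mg, true response 15% v 50%, two-sided Fisher test at 0.05.

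| At exactly 35 mg, per arm | Left per arm | Power |
|---|---|---|
| 0 | 20 | 57% |
| 2 | 18 | 50% |
| 5 | 15 | 37% |
| 9 | 11 | 25% |

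**3. Table 9 coding over the whole ITT set.** *Assumed:* 10/20 v 3/20 responders in the ≤35 mg subset, and 25 per arm in the <40 mg stratum.

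| Denominator | Rates | Fisher p | Odds ratio |
|---|---|---|---|
| ≤35 mg subset, 20 per arm | 50% v 15% | 0.041 | 5.67 |
| ITT, dose stratum respected (only the 25 per arm at <40 mg inform) | 40% v 12% in that stratum | 0.051 | 4.89 |
| ITT, unstratified, 45 per arm | 22% v 7% | 0.069 | 4.00 |

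Under this coding every subject at ≥40 mg is a non-responder by construction, so that stratum adds nothing to a stratified test. The p-value therefore moves little, but the ITT rates are less than half the subset rates.

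**4. Does the model text settle the denominator?** No. The logistic model in 12.5.1.1 applies to every secondary endpoint and includes the <40/≥40 dose group, as does the imputation model in 12.5.1.2. Section 12.5.2 plans a baseline-dose subgroup for 2.2. Within a ≤35 mg subset the dose group has one level, so the text was not adapted to the subset. By contrast, 12.5.1 spells out the restricted denominator for 2.3.

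**The case against.** The mg/m² wording sits in descriptive text that itself refers to Table 5. Table 5 is what 9.6 names for Hochberg testing, and the absolute cut appears in many more places. A careful programmer would probably follow it. SAP 9.7 is a subgroup list and resembles the supportive <35/≥35 split in protocol 9.4.9. The Table 9 row label and 12.5.1 both point to the subset, and naming the ITT set in 12.5 is compatible with a subset of it. This is why the denominator is an ambiguity and not a stated rule. It does not excuse the unit and the inequality, which are tied by endpoint number to 2.2 and 3.7 and contradict Table 5 outright.

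The p-value illustration is also fragile. With 9 v 3 responders the result is non-significant at 20, 25 and 45 per arm (0.082, 0.095, 0.118); with 11 v 3 it is significant at all three (0.019, 0.025, 0.039). Fisher is only the fallback in 12.5.1.1, and under Hochberg with three endpoints p = 0.041 succeeds only if it is not the largest of the three by too wide a rule: it needs both other p-values to be ≤0.05. That stands, and the case does not rest on crossing 0.05.

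Finally, a covariate that is constant in the subset does no harm, and the minimum of 10 subjects per subgroup in 9.7 already disposes of the empty dose subgroup. That stands too: the model term is a tidying matter.

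**Conclusion.** The concern holds and should be fixed before database lock. The contradiction in unit (5.1.2.1 and 5.1.3.5) and in inequality (9.7) is plain in the text, and Table 9 with 12.5 leaves the denominator open.

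The unit error is the largest: at BSA of 1.71 m² or more it removes the restriction entirely, and this needs no assumption beyond the eligibility cap. The 59% to 95% range depends on the assumed BSA and dose distributions. The fall in power from 57% to as low as 25% depends on the assumed subset size, response rates and number of subjects at exactly 35 mg. The Table 9 coding mainly affects the reported rates and has little effect on the specified stratified test. Endpoint 3.7 is exploratory and outside the Hochberg family, and the primary endpoint is not touched.

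**What to change.** Align everything to Table 5:

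1. In SAP 5.1.2.1 and 5.1.3.5, change the unit of the 35 baseline cut from mg/m²/day to mg/day. Leave the 11 mg/m²/day response target as it is.
2. In SAP 9.7, change the entry for 2.2 and 3.7 to ≤35 mg/day. If the protocol's <35/≥35 supportive split is still wanted, list it separately without tying it to these endpoints.
3. In Table 9 and 12.5, define the 2.2 and 3.7 indicators and denominators only for ITT subjects with baseline ≤35 mg/day, and state that all others are excluded and not coded 0. The 2.3 text in 12.5.1 is a model for this.
4. As tidying, for 2.2 and 3.7 drop the <40/≥40 term from the models in 12.5.1.1 and 12.5.1.2 and drop the baseline-dose subgroup in 12.5.2. This needs matching exceptions in 9.1, which uses both strata in all efficacy analyses, and in 12.6.3 with its subsections, through which 3.7 is analysed.

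The cost is SAP wording before lock; no new data are needed.
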